8.3.13.14 Intraocular pressure (IOP) measurement

Intraocular pressure will be measured using three techniques. Goldmann Applanation Tonometry (GAT) will be performed in the clinic at every visit and if available, Pascal Dynamic Contour Tonometry (DCT) at V05 through V09. ARGOS-SC measurements will be performed in the clinic at every visit and by the patient at home between the visits. Only GAT will be used to guide any treatment decisions. The GAT and DCT must be performed by as few dedicated investigators as possible at each site to reduce potential bias.

IOP measurement in the clinic

IOP measurement will be conducted at V02 through V09 as a series of 2x GAT (in case of a difference of more than 2mmHg, a third GAT-measurement is required) followed by 3x ARGOS-SC system. When series of measurements are made, GAT must always be used first to avoid potential operator bias. For the ARGOS-SC measurements the patient has to stay in the same position as for the GAT-measurements (chin on chin rest, forehead installed). From V05 through V09 additionally (if available), a series of 2x DCT (in case of a difference of more than 2mmHg, a third DCT-measurement is required)

followed by 3x ARGOS-SC will be performed after the series of GAT and ARGOS-SC measurements. For the ARGOS-SC measurements, the patient has to stay in the same position as for the DCT-measurements (chin on chin rest, forehead installed).

Optional: At V06, V07 and V09, the patient will be hospitalized for 24-hours measurements with GAT and ARGOS-SC. IOP measurements with ARGOS-SC will be done automatically via an external antenna. IOP measurements with GAT will be done every three hours, if it is possible even at night. If night measurements are not possible every three hours at night, the last measurement should take place between 22 and 24 o'clock and the three-hours rhythm should be resumed between 5 and 7 o'clock on the next morning.

ARGOS-SC system measurement by the subject at home

Subjects will receive detailed instruction in the use of the MESOGRAPH reading device. At V02, they will receive an individual MESOGRAPH reading device, a copy of the instructions for use and the Multiline Connector to perform self-tonometry at home. Subjects will be requested to perform at least 4 IOP measurements daily with the MESOGRAPH, one each in the morning after getting up, at noon, in the afternoon and in the evening before going to bed.

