2.8 Study variables

2.8.1 Primary performance parameters

- GAT measurements (2 3 measurements) at visit V02 V09
- ARGOS-SC system measurements (2 3 measurements) at visit V02 V09 roughly contemporaneous with the GAT measurements
- Pascal DCT (2 3 measurements) at visit V05 V09 (if available)
- ARGOS-SC system measurements (2 3 measurements) at visit V05 V09 roughly contemporaneous with the Pascal DCT measurements

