2.9 Study endpoints

2.9.1 Primary endpoints

Performance:

Level of agreement between measurements made using GAT and the ARGOS-SC system at visit V02 - V09.

The concordance of the intraindividual measurement values of GAT and ARGOS-SC will be indicated by the concordance correlation coefficient r_{ccc} (4.6.1), separate for each visit

Additionally, the absolute difference between the GAT and ARGOS-SC measurement will be scaled in \leq 5mmHg and > 5 mmHg and the frequency distribution will be displayed (4.6.1, Table 2).

The Bland-Altman (mean-difference) plot and a X-Y plot should illustrate the comparison of the two methods (4.6.1, Figure 1).

The level of agreement between Pascal DCT and ARGOS-SC will be evaluated analogously.

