4.6 Analysis of endpoints

4.6.1 Performance endpoints

The evaluation uses the following methods to analyze the agreement between two different measurement methods

Bland-Altman Plot:

Bland and Altman introduced the Bland-Altman plot to describe agreement between two quantitative measurements by constructing limits of agreement. These statistical limits are calculated by using the mean and the standard deviation (s) of the differences between two measurements. To check the assumptions of normality of differences and other characteristics, they used a graphical approach.

The resulting graph is a scatter plot XY, in which the Y axis shows the difference between the two paired measurements (x-y) and the X axis represents the average of these measures ((x+y)/2). In other words, the difference of the two paired measurements is plotted against the mean of the two measurements. Bland-Altman recommended that 95% of the data points should lie within \pm 2s of the mean difference. This is the most common way to plot the Bland-Altman method.

The bias is computed as the value determined by one method minus the value determined by the other method. If one method is sometimes higher, and sometimes the other method is higher, the average of the differences will be close to zero. If it is not close to zero, this indicates that the two assay methods are systematically producing different results.

Concordance correlation coefficient

Concordance correlation coefficient (r_{ccc}) measures the agreement between two variables X and Y. Lawrence Lin has defined the form of the concordance correlation r_{ccc} as^[1]

$$r_{ccc} = 2 r s_x s_y / ((s_x^2 + s_y^2) + (m_x - m_y)^2)$$

with

 $r = s_{xy}/(s_x s_y)$ (Pearson correlation coefficient)

 m_x = mean of X

 $m_y = mean of Y$

 s_x = standard deviation of X

 s_y = standard deviation of Y

 s_{xy} = covariance of x and Y

The concordance correlation r_{ccc} has an range of -1 to 1. Values near +1 indicate strong concordance between x and y, values near -1 indicate strong discordance and values near zero indicate no concordance. There is no clear-cut agreement as to how to interpret the values, although one approach is to interpret Lin's r_{ccc} as for Pearson's correlation coefficient (e.g. values less than .20 are poor, while values greater than .80 are excellent).

The following values will be calculated:

- Calculation of the average of the (up to) 3 IOP measurements using GAT (GAT_{mean})

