- Calculation of the average of the (up to) 3 IOP measurements using ARGOS-SC (ARGOS1_{mean})
- Calculation of the average of the (up to) 3 IOP measurements using DCT (DCT_{mean})
- Calculation of the average of the (up to) 3 IOP measurements using OPA (OPA_{mean})
- Calculation of the average of the (up to) 3 IOP measurements using ARGOS-SC (ARGOS2_{mean})
- Difference IOP_{d1}= ARGOS1_{mean} GAT_{mean}
- Mean IOP_{mean1} = (ARGOS1_{mean} + GAT_{mean})/2
- Difference IOP_{d2}= ARGOS2_{mean} DCT_{mean}
- Mean IOP_{mean2} = (ARGOS2_{mean} + GAT_{mean})/2

 $ARGOS1_{mean}$ / GAT_{mean} / IOP_{d1} (statistical parameters, concordance correlation coefficient r_{ccc} , Bland-Altman-Plot with IOP_{mean1} vs. IOP_{d1} , plot of $ARGOS1_{mean}$ vs. GAT_{mean}), separate for each visit

 $|IOP_{d1}| \leq 5 \text{ mmHg (N, \%)}$

ARGOS2_{mean} / DCT_{mean} / IOP_{d2} (statistical parameters)

 $|IOP_{d2}| \leq 5 \text{ mmHg (N, \%)}$

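### SAP 4.6.1 pairs the ARGOS-DCT difference with an ARGOS-GAT mean, so the implied ARGOS-DCT Bland-Altman plot would have wrong x-values (minor formula correction)

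*SAP*

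**What the plan says.** SAP 4.6.1 lists the quantities to be derived for each method comparison.

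- **GAT comparison.** IOP_d1 is ARGOS1 minus GAT, and its average is "Mean IOP_{mean1} = (ARGOS1_{mean} + GAT_{mean})/2". Both lines use the same two methods.
- **DCT comparison.** IOP_d2 is ARGOS2 minus DCT, but its average is "Mean IOP_{mean2} = (ARGOS2_{mean} + GAT_{mean})/2".

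The Bland-Altman description in the same section defines the plot by the two measurements being compared: the y-axis is their difference and "the X axis represents the average of these measures ((x+y)/2").

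SAP 2.8.1 describes the second ARGOS-SC series, V05 to V09, as "roughly contemporaneous with the Pascal DCT measurements". Protocol 8.3.13.14 fixes the order: the DCT readings "followed by 3x ARGOS-SC will be performed after the series of GAT and ARGOS-SC measurements".

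On outputs, SAP 2.9.1 asks for the concordance coefficient, the 5 mmHg split, a Bland-Altman plot and an X-Y plot for GAT, and then says: "The level of agreement between Pascal DCT and ARGOS-SC will be evaluated analogously". The output lines in 4.6.1 are shorter for DCT. They give "ARGOS2_{mean} / DCT_{mean} / IOP_{d2} (statistical parameters") and the count within 5 mmHg, and name no plot and no concordance coefficient.

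**The concern.** The index 2 joins a DCT difference to a GAT average. ARGOS2 and GAT are not a designated pair: GAT belongs with the first ARGOS-SC series, and the second series is taken later, after DCT. Neither document gives a reason for bringing GAT into the DCT comparison.

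Agreement with DCT from V05 to V09 is part of the primary objective (protocol 7.1.1) and of the primary endpoint (protocol 8.1.3.1). One use of a Bland-Altman plot is to see whether the difference changes with the level of IOP. Protocol 8.2.2 says that DCT is meant to remove some of GAT's corneal errors and is believed to be nearer true IOP, especially at high pressures. If so, GAT - DCT is not constant across the pressure range. Putting GAT into the x-value would then bring GAT's errors into the figure for the comparator chosen to avoid them, and could distort the trend the figure is read for.

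**Working it through.** The plan states no numerical result here, so there is no figure to reproduce. The check is algebra, followed by an illustration with assumed error sizes. Write A for ARGOS2_mean, D for DCT_mean and G for GAT_mean.

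**1. Shift of each point**

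- x as written: (A + G)/2
- x by the SAP's own rule: (A + D)/2
- Difference: (A + G)/2 - (A + D)/2 = (G - D)/2

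Example with invented values A = 18, D = 16, G = 20: the plotted difference is 18 - 16 = 2. The x-value is (18 + 20)/2 = 19 as written and (18 + 16)/2 = 17 by the rule. The shift is 2 = (20 - 16)/2.

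**2. Size of the shift**

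The documents give no GAT-DCT difference. Over an assumed range:

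| G - D (mmHg) | Shift in x (mmHg) |
|---|---|
| 1 | 0.5 |
| 2 | 1.0 |
| 3 | 1.5 |
| 5 | 2.5 |

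Negative differences give the same shifts with the opposite sign. For scale, 2 mmHg is the limit in the repeat rule of protocol 8.3.13.14 ("in case of a difference of more than 2mmHg, a third GAT-measurement is required"), and 5 mmHg is the imprecision of repeated IOP readings quoted in protocol 3.2. Neither is an estimate of G - D.

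**3. Effect on the slope**

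If G - D equals a constant c, every x moves by c/2 and the fitted slope of the difference on x does not change.

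If G - D varies from point to point, the slope can change, and ordinary measurement error is enough. Let each method equal true IOP (variance V) plus a fixed offset plus independent error, with error variances a, d and g for ARGOS, DCT and GAT.

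- Correct x: slope = [(a - d)/2] / [V + (a + d)/4]
- x as written: slope = (a/2) / [V + (a + g)/4]

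With the correct mean, equal ARGOS and DCT errors cancel and the slope is zero. With GAT in x, the ARGOS error sits in both axes and nothing offsets it. Take an assumed true-IOP SD of 4.5 mmHg, so V = 20.25:

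- Error SD 2 mmHg for all three methods: correct slope 0; slope as written 2/(20.25 + 2) = 2/22.25 = 0.09.
- Error SD 3 mmHg for all three methods: correct slope 0; slope as written 4.5/(20.25 + 4.5) = 4.5/24.75 = 0.18.

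A simulation of one million points under the same assumptions, with offsets of -1 mmHg for GAT and +1 mmHg for DCT, gave 0.00 against 0.090 and 0.00 against 0.183. Over a 10 mmHg span of IOP, slopes of 0.09 and 0.18 would look like trends of 0.9 and 1.8 mmHg where none exists.

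**4. Could it be seen in this trial?**

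There are at most 24 points per visit and 24 x 5 = 120 over V05 to V09. With 24 points (22 df), a correlation must exceed 0.344 at two-sided 0.10, or 0.404 at two-sided 0.05, to differ from zero. Multiplying the slope by SD(x)/SD(difference) gives the correlations for the two cases:

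- 0.0899 x 4.717/2.828 = 0.15
- 0.1818 x 4.975/4.243 = 0.21

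Both fall below the threshold, so at a single visit the distortion would be hard to tell from chance.

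**5. What does not change**

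Bias, the SD of the difference, the limits of agreement and the share within 5 mmHg depend only on A - D. The concordance coefficient depends on A and D. The success criterion in protocol 9.5 uses GAT and ARGOS-SC. None of them uses IOP_mean2.

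**The case against.** The mismatch itself is hard to dispute. The case against giving it weight has four parts.

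- **No listed output uses IOP_mean2.** The DCT lines in 4.6.1 need only the difference, and the plot comes from reading 2.9.1's instruction for DCT as covering the GAT figures. This is true, and it caps the severity. But the only use the SAP makes of the GAT counterpart, IOP_mean1, is as the x-axis of that plot, so defining IOP_mean2 points to the same plot for DCT. If no plot is wanted, the SAP holds an unused and wrong variable and the two sections still need reconciling.
- **A programmer could infer the right formula** from the general rule and from the IOP_mean1 line. Probably so, but an explicit formula is what usually gets programmed.
- **No conclusion of the trial changes.** This stands in full.
- **The evidence for a trend is weak for this pair.** Protocol 4.9.1 reports that differences grew with IOP for the related EYEMATE-IO sensor against GAT, not DCT, and DCT may show less of a trend. This also stands. The argument here rests on G - D varying, not on an expected ARGOS-DCT trend.

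In addition, the SAP plans no test of the difference against the mean, so the correlation thresholds above only show how little 24 points can resolve.

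**Conclusion.** The formula is wrong as written: it contradicts the SAP's own Bland-Altman definition, its IOP_mean1 line and the pairing of the second ARGOS-SC series with DCT. The shift of (GAT - DCT)/2 per point is exact. Its size in mmHg and the false slopes of 0.09 and 0.18 rest on assumed values, because the documents give no GAT-DCT differences or error SDs.

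The point is minor. It affects the x-axis of one implied figure. DCT is taken only where available (protocol 8.2.1), so that figure may hold fewer than 24 points per visit. The shorter DCT output list in 4.6.1 is a wording gap against 2.9.1, and the conclusion does not depend on it.

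**What to change.** In SAP 4.6.1, change the formula to `IOP_mean2 = (ARGOS2_mean + DCT_mean)/2`.

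In the same section, bring the DCT outputs into line with 2.9.1. State that the ARGOS2/DCT pair, at V05 to V09 and separately for each visit, also gets the concordance coefficient, the Bland-Altman plot of IOP_mean2 against IOP_d2 and the X-Y plot, in addition to the statistical parameters and the 5 mmHg share already listed.

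The cost is one term in a formula, one output line and the matching program lines. No new data are needed, and no other planned result changes.

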4.6.2 Safety endpoints

Incidences of adverse events stratified by:

- expectedness: expected event / unexpected event (N, %)
- severity: mild / moderate / severe (N, %)
- causal relationship to medical device: none / unlikely / possible / probable / definite (N, %)
- causal relationship to other: none / unlikely / possible / probable / definite (N, %)
- seriousness: yes / no (N, %)
- outcome: recovered / recovered with sequelae / recovering / not recovered / death / unknown (N, %)

(if indicated).

Incidences of device deficiency stratified by:

- involved component: ARGOS-SC sensor / MESOGRAPH reader (N, %)
- did this device deficiency involve the patient: no / yes (N, %)
- consequences of the device deficiency (ARGOS-SC sensor): none / recalibration / discontinued use / explanation (N, %)
- consequences of the device deficiency (MESOGRAPH reader): none / discontinued use / discontinued use with a replacement device (N, %)

4.6.3 Further endpoints

- User acceptance of the ARGOS-SC implantation procedure by means of evaluation of implantation procedure questionnaires (investigators) at V01 (statistical parameters)
- User acceptance of the ARGOS-SC system at the investigational site by means of evaluation of patient acceptance questionnaires (by investigators) at V09 (statistical parameters)
- User acceptance of the ARGOS-SC system at home by means of evaluation of patient acceptance questionnaires (patients) at V09 (statistical parameters)
- Repeatability of the ARGOS-SC measurement (statistical parameters)
- Concomitant glaucoma medication is shown separately as follows:
 - Previous glaucoma medication (stopped before implantation): in total (N,%) and stratified by ingredients (N, %) (Mock-up Table 3a)
 - Concomitant glaucoma medication (medication given during V01 V09): in total (N, %) and stratified by ingredients (N, %) (Mock-up Table 3b)

- Other concomitant medication is shown separately as follows:
 - Previous medication (stopped before implantation): in total (N, %) and stratified by ingredients (N, %)
 - Concomitant medication (medication given during V01 V09): in total (N,
 %) and stratified by ingredients (N, %)
- NEI VFQ-25 questionnaire:
 - 25 items in course of study (statistical parameters)
 - 12 sub-scales in course of study (statistical parameters)
 - Changes from baseline of the 12 sub-scales (statistical parameters)

The changes from baseline of the 12 sub-scales will be analysed by means of paired t-Test (in case of normal distribution) or the Wilcoxon sign rank test (in case of non-normal distribution). The Mixed Model repeated measurement (MMRM) analysis of covariance for repeated measures in mixed models (V06, V07, V09 vs. Screening) will be used in addition.

 Daily IOP self-measurement profiles (patients) will not be included into the evaluation.

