9.3 Level of significance and the power of the clinical investigation

Significance level is set to 0.10, Power to 80%.

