2.9.3 Further endpoints

NEI VFQ-25 questionnaire:

The 25 items will be converted to a 0 (= worst response) to 100 scale (= best response). Then, the items within sub-scale will be averaged to create 12 sub-scale scores:

- General health (1 item: question 1)
- General vision (1 item: question 2)
- Ocular pain (2 items: question 4 and 19)
- Near activities (3 items: question 5, 6, and 7)
- Distance activities (3 items: question 8, 9, and 14)
- Vision specific: Social functioning (2 items: question 11 and 13)
- Vision specific: Mental health (4 items: question 3, 21, 22 and 25)
- Vision specific: Role difficulties (2 items: question 17 and 18)
- Vision specific: Despendency (3 items: question 20, 23 and 24)
- Driving (2 items: question 15c, 16)
- Color vision (1 item: question 12)
- Peripheral vision (1 item: question 10)

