4.1.4 Level of significance

All statistical test will be performed with a two-tailed alpha (α) of 0.10, all confidence intervals which will be calculated will be 95% confidence intervals.

Test results p<0.05 will be regarded as 'significant', test results with p-values p<0.10 as 'remarkable' or as 'trends / tendencies'.

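### SAP 4.6.3 plans 36 unadjusted VFQ-25 contrasts and 4.1.4 calls each p<0.05 significant, so with no true change a false label on this further endpoint has a chance of roughly 33% to 84%

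*SAP*

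**What the plan says.** SAP 2.9.3 (Further endpoints) converts the 25 items to a 0–100 scale, after which "the items within sub-scale will be averaged to create 12 sub-scale scores". The SAP flow chart (2.10) has the questionnaire at Screening, V06, V07 and V09. SAP 4.2 defines change from baseline visit by visit.

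The tests are in SAP 4.6.3: "The changes from baseline of the 12 sub-scales will be analysed by means of paired t-Test (in case of normal distribution". Where the changes are not normally distributed, a Wilcoxon signed-rank test takes the place of the t-test. A mixed model follows: "repeated measures in mixed models (V06, V07, V09 vs. Screening) will be used in addition". The section does not say which result stands if the two analyses differ, whether the model yields one p-value per visit or an overall one, or whether the Screening value enters as a covariate or as a response.

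The labels come from SAP 4.1.4: "All statistical test will be performed with a two-tailed alpha (α) of 0.10", and then "Test results p<0.05 will be regarded as 'significant', test results with p-values p<0.10 as 'remarkable' or as 'trends / tendencies". The same section sets all confidence intervals at 95%. Protocol 9.3 also gives a level of 0.10 but ties it to no hypothesis.

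Neither document mentions multiplicity or names a primary VFQ-25 sub-scale, composite or visit. VFQ-25 is not among the primary and secondary endpoints (Protocol 8.1.3) or in the success rule (Protocol 9.5). Protocol 8.3.7 calls the whole investigation exploratory.

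**The concern.** The SAP attaches a verdict word to each p-value and then produces many of them on one questionnaire. With 36 contrasts at a per-test level of 5%, the expected number of false *significant* results is 36 × 0.05 = 1.8. At 10% the expected number of results under one label or the other is 36 × 0.10 = 3.6. A report that follows the SAP to the letter could therefore carry a *significant* change in, say, near activities at day 180 when nothing has happened.

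This is a single-arm study in which the implant is placed during glaucoma surgery. A stray label cannot be checked against a control group, and it could be taken as a benefit or a harm of the device. What is at stake is how a further endpoint is reported.

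**Working it through.** **No figure to reproduce.** The documents give no sample size, power or family-wise error for VFQ-25. The approximate 120 measurements in Protocol 9.2 concern IOP pairs and do not bear on this point.

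**Inputs from the documents.** 12 sub-scales (SAP 2.9.3); 3 visits against Screening (SAP 4.6.3, 4.2); thresholds 0.05 and 0.10, two-sided (SAP 4.1.4); 24 patients (Protocol 8.3.7).

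**Assumptions.** No true change in any sub-scale; normally distributed changes; paired t-tests; complete data. The correlations are not in the documents, so they are varied: 0 to 0.8 between sub-scales, 0.5 to 0.85 between the changes at different visits.

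**Step 1, independent tests.** Chance of at least one false result = 1 − (1 − α)^m.
- m = 36, α = 0.05: 1 − 0.95^36 = 0.842
- m = 36, α = 0.10: 1 − 0.90^36 = 0.977
- m = 12 (one visit), α = 0.05: 1 − 0.95^12 = 0.460

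The 84% is an upper reference. The three changes for a sub-scale share the same Screening value. If scores at all visits have equal variance and a common correlation ρ, two changes have covariance 1 − ρ and variance 2(1 − ρ), so their correlation is 0.5 whatever ρ is.

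**Step 2, correlated tests.** Simulation of 36 paired t-tests, n = 24, 6,000 runs per row (Monte Carlo standard error at most √(0.25/6000) = 0.006). Each column is the chance of at least one such result.

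| Sub-scale corr. | Visit corr. | p<0.05 | p<0.10 | p<0.05, improvement only | p<0.05, V09 only |
|---|---|---|---|---|---|
| 0 | 0.5 | 81% | 96% | 55% | 45% |
| 0.3 | 0.5 | 74% | 93% | 43% | 39% |
| 0.5 | 0.5 | 65% | 87% | 36% | 33% |
| 0.5 | 0.85 | 51% | 76% | 26% | 32% |
| 0.7 | 0.5 | 52% | 74% | 26% | 25% |
| 0.7 | 0.85 | 40% | 62% | 20% | 24% |
| 0.8 | 0.5 | 42% | 65% | 22% | 19% |
| 0.8 | 0.85 | 33% | 52% | 17% | 20% |

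A separate run at 0.8/0.8 gives 34% and 54% for the first two result columns. With n = 17 the figures are similar.

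**Step 3, the second method.** A visit contrast adjusted for Screening stood in for the mixed model. Counting a hit by either method gives 69% to 82% at sub-scale correlation 0.5 and 47% to 61% at 0.8. Much of this rise comes from the stand-in's own per-test error of 5% to 9%, because it treats baseline as fixed. These figures therefore only show that the unspecified model matters; they do not measure the SAP's mixed model.

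**Step 4, what controls it.** Bonferroni over 36 contrasts (p<0.05/36 = 0.0014), or over 12 sub-scales at one visit with one method (p<0.05/12 = 0.0042), holds the family-wise error to at most 5% (simulated 2% to 5%). Fixing the visit and method alone, without adjustment, does not: see the last column.

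**The case against.** The strongest reply is that this is a third-tier outcome in a study the protocol calls exploratory. VFQ-25 appears in no objective, no claim to be verified and no success criterion, and a nominal p-value in such a table is not a claim. That stands, and it limits the point to reporting. It does not remove it: SAP 4.1.4 assigns *significant* to these tests without qualification. The protocol marks the acceptance questionnaires as exploratory only (8.3.12, 8.3.13.6) but puts no such wording on VFQ-25 (8.3.13.7).

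A reader might infer more than the documents support:

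- *A false quality-of-life claim is more likely than not.* No such claim is planned. Whether the chance of a false label at p<0.05 exceeds one half depends on correlations that the documents do not give. It falls below one half when sub-scales correlate strongly and for V09 alone. For a false improvement it exceeds one half only when sub-scales are close to uncorrelated.
- *There are 72 p-values to choose from.* SAP 4.6.3 selects t-test or Wilcoxon by normality and adds the mixed model as a supplement on the same data. Its output is not specified, so 36 further p-values cannot be read into it.
- *This is the only place where the SAP can yield a significant result.* SAP 4.1.7 leaves subgroup analyses to a later data review meeting, and 3.5 plans normality tests on every continuous parameter.

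Two further objections have weight. The simulation is not the SAP's exact procedure: four sub-scales are single items with discrete scores, for which Wilcoxon may be used, and missing data are not replaced. The percentages are therefore approximate. Formal adjustment also has a price. At n = 24 and an assumed standardised change of 0.6, paired-t power falls from 0.80 at p<0.05 to 0.43 at p<0.0042; at 0.5 it falls from 0.65 to 0.26. That would also mask deterioration in a first-in-human implant.

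**Conclusion.** The point holds as a reporting fault. The labelling rule in SAP 4.1.4, applied to the 36 contrasts of 4.6.3, has a chance of roughly 33% to 81% of producing at least one false *significant* VFQ-25 label under the assumed correlations, with 84% as the independent-test figure. For p<0.10 the range is roughly 52% to 98%. Even the lowest value is more than six times the nominal 5% (0.327/0.05 = 6.5). These figures rest on no true change, normal data, 24 complete patients and one method.

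The trial's pass/fail verdict is unaffected. Removing the false labels would still not allow a real change to be attributed to the device, since there is no control group. The change is worth making because a stated rule misleads and correcting it costs almost nothing.

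**What to change.** - **SAP 4.6.3:** name one method as the VFQ-25 analysis, for example the mixed model, and state how the Screening value enters it. Report the change at V06, V07 and V09 for each sub-scale as an exploratory, unadjusted estimate with a 95% interval. State that the intervals are unadjusted, so that one excluding zero is not read as a test result.
- **SAP 4.1.4:** add that *significant*, *remarkable* and *trend* are not used for VFQ-25 results.

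Holm adjustment over the 12 sub-scales at V09 is needed only if the sponsor wants a confirmatory quality-of-life statement, and it carries the power loss shown above.

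The cost is SAP wording alone; no visit, patient or data item changes. The downside is that no single sub-scale can be called significant.
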